7.4.2. Concomitant Medication

Concomitant medications will be presented in two separate summary tables: concomitant medications received during the Treatment Period of HZNP-TEP-302 (up to and including 21 days after the last dose of study drug) and concomitant medications received during the Follow-Up Period HZNP-TEP-302 (the period after 21 days following the last dose of

study drug). Any medication that is ongoing or has a stop date on or after the first dose date will be considered a concomitant medication. Any concomitant medication that has a start date, stop date or is ongoing on or after the first dose but prior to 21 days following the last dose of study drug will be considered a concomitant medication during the Treatment Period. Any medication that is ongoing or has a stop date after 21 days following the last dose of study drug will be considered a concomitant medication during the Follow-Up Period. As such, the same medication may be summarized as both prior and concomitant during either or both periods. The summary tables will not be mutually exclusive.

Further, a separate summary of concomitant medications during the Follow-Up Period and Follow-Up Contact Period will be provided for TED medications. TED medications during the Follow-Up Period will be identified by a manual listing review prior to generating the primary study analyses (Week 48).

Missing date imputation rules are provided in Section 6.3.3.

7.4.3. Concomitant Procedures

A listing will be provided for subjects undergoing any concomitant procedures performed during the Treatment Period of HZNP-TEP-302 (up to and including 21 days following last dose of study drug). TED concomitant procedures during the Follow-Up Period will be identified in the listing. TED procedures during the Follow-Up Period will be identified by a manual listing review prior to generating the primary study analyses (Week 48).

7.4.4. Follow-Up Contact Thyroid Eye Disease Surgeries, Orbital Radiation, and Follow-up Treatments

A summary will be provided of the count and percent of subjects receiving no additional TED treatment (medication, procedure, surgery, and/or orbital radiation treatment), at least one additional TED treatment, at least two additional TED treatments and three or more additional TED treatments during the Follow-up Period and Follow-Up Contact Period. Separate listings will be provided for subjects undergoing any TED surgical procedures, orbital radiation, and Follow-Up treatments.

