##### **9.5.6.15.2 Month 18 – Follow-Up Contact for Subjects Who Relapsed in Study HZNP-TEP-301**

Subjects who complete the Week 24 Visit will be contacted 12 months later via phone or email by research staff to enquire if any treatment for TED has been received since last study contact. If yes, subject will be questioned regarding type of treatment and outcome/response.

This is the final contact for subjects who relapsed in Study HZNP-TEP-301.

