##### **9.5.6.16 Month 24 – Follow-Up Contact for Proptosis Non-responders in Study HZNP-TEP-301**

Subjects who complete the Month 12 Visit will be contacted 12 months later via phone or email by research staff to enquire if any treatment for TED has been received since last study contact. If yes, subject will be questioned regarding type of treatment and outcome/response.

This is the final contact for proptosis non-responders in Study HZNP-TEP-301.

The end of the trial is defined as the date of the last subject contact at Month 24.

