After completion of the Treatment Period, subjects who were proptosis non-responders in Study HZNP-TEP-301 will enter a 24-week Follow-Up Period, during which study drug will not be administered and clinic visits are scheduled for 1, 3, and 6 months (Visits Month 7, 9 and 12) after the Week 24 visit; if any of these subjects discontinue from the Follow-Up Period prior to the Month 12 Visit, they will return to the clinic and undergo the scheduled Month 12 assessments prior to study discharge. Those who complete the Month 12 visit will be contacted at 6 and 12 months later via phone or email by research staff to enquire if any treatment for TED has been received since last study contact. If yes, subject will be questioned regarding type of treatment and outcome/response.

Subjects who relapse during the Follow-Up Period of HZNP-TEP-301 and choose to enter this extension study will not participate in the Follow-Up Period. For these subjects, the last clinic visit is at Week 24. Those who complete the Week 24 visit will be contacted 6 and 12 months later via phone or email by research staff to enquire if any treatment for TED has been received since last study contact. If yes, subject will be questioned regarding type of treatment and outcome/response.

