6. GENERAL ASPECTS FOR STATISTICAL ANALYSIS

6.1. GENERAL METHODS

The following conventions will be utilized in the analyses:

- In general, descriptive summaries will be provided by treatment received in HZNP-TEP-301 and overall.
- The following treatment group labels will be used: “HZNP-TEP-301 Placebo” for subjects who were randomized to Placebo in HZNP-TEP-301 and “HZNP-TEP-301 HZN-001” for subjects who were randomized to HZN-001 in HZNP-TEP-301.
- Unless otherwise indicated, continuous variables will be summarized using the number of observations (n), mean, standard deviation (SD), median, minimum (min), and maximum (max). Categorical variables will be summarized using number of observations (n), frequency and percentages of subjects.
- The same number of decimal places as the raw data will be presented when reporting min and max, 1 more decimal place than in the raw data will be presented when reporting mean and median, and 2 more decimal places than in the raw data will be presented when reporting SD.
- If multiple assessments occur at a given time point, the latest value will be used. If multiple assessments occur on the same day and the time is not recorded, the average of the values will be used in any descriptive summaries.
- All relevant subject data will be included in listings. All subjects entered into the database will be included in subject data listings.
- Additional programming considerations are provided in Section 14.

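### The count of additional TED treatments in SAP 7.4.4 mixes 72-week and 48-week follow-up, observed under different conditions, and should be split by enrollment type

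*SAP*

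**What the plan says.** SAP 7.4.4 plans a count and percentage of subjects with no additional TED treatment, at least one, "at least two additional TED treatments and three or more additional TED treatments during the Follow-up Period and Follow-Up Contact Period". Treatment here covers medication, procedure, surgery and orbital radiation. The section names no columns, cut-off, person-time rate or split by enrollment type. The table index lists one ITT table, 14.1.4.1.2.4. SAP 6.1 supplies the default layout: "In general, descriptive summaries will be provided by treatment received in HZNP-TEP-301 and overall".

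The two enrollment types have different schedules (SAP 3.4):

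- Lead-in proptosis non-responders "will enter a 24-week Follow-Up Period, during which study drug will not be administered". Then: "Those who complete the Month 12 visit will be contacted at 6 and 12 months later via phone or email by research staff". Protocol 9.5.6.16 says of Month 24: "This is the final contact for proptosis non-responders in Study HZNP-TEP-301".
- Relapse subjects who "choose to enter this extension study will not participate in the Follow-Up Period" have their last clinic visit at Week 24. Then: "Those who complete the Week 24 visit will be contacted 6 and 12 months later via phone or email". Protocol 9.5.6.15.2 says of Month 18: "This is the final contact for subjects who relapsed in Study HZNP-TEP-301".

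SAP 6.6 lists enrollment type as a subgroup but provides subgroup summaries only for efficacy endpoints and TEAEs. Protocol Table 9.1 restricts orbital irradiation and eye surgery for TED through Week 48 of follow-up, and steroids for TED through the end-of-study visit.

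**The concern.** A cumulative count can only rise as observation lengthens. When one group is followed longer and the groups are pooled, the percentage reflects follow-up as well as need for treatment.

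The contrast in follow-up lies between enrollment types, but it can carry over into the prior-treatment columns. Inclusion criterion 3 and Protocol 9.3.4 make a Week 24 response a condition of relapse. Relapse subjects are therefore likely to be commoner among those who had teprotumumab in the lead-in study, and non-responders among those who had placebo. The prior-teprotumumab column would then have the shorter average window and could appear to need less further treatment at equal underlying need. The table is a natural place to look for durability, so a reader could take that difference as real.

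Other parts of the SAP deal with the difference. Sustained response is confined to lead-in non-responders (8.1, 8.2.1, 8.2.3, 8.3.1). Follow-up AE denominators use subjects who enter the Follow-Up Period (10.3). Exposure and compliance are also shown by enrollment type (10.1, 10.2). Section 7.4.4 has no such provision.

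**Working it through.** **Step 1. Reproduce the stated length of the contact period.** The Schedule of Assessments gives 48 weeks.

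- Non-responders: Week 96 − Week 48 = 48 weeks.
- Relapse subjects: Week 72 − Week 24 = 48 weeks.

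Both agree.

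**Step 2. Scheduled observation after Week 24.**

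| | Clinic follow-up | Contacts | Total | Range with visit windows |
|---|---|---|---|---|
| Non-responders | 24 wk | 48 wk | 72 wk | 69–75 wk |
| Relapse subjects | 0 | 48 wk | 48 wk | 45–51 wk |

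The ratio is 72/48 = 1.5. The range allows ±7 days at Week 24 and ±14 days at the last contact, 3 weeks in all. Subjects who do not complete Month 12 (non-responders) or Week 24 (relapse) are not scheduled for contact, so their observation is shorter.

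**Step 3. Effect on the count if one constant rate applied to everyone (assumption).** If p48 is the percentage with at least one treatment by 48 weeks, then p72 = 1 − (1 − p48)^(72/48).

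| p48 (assumed) | p72 | Difference |
|---|---|---|
| 10% | 14.6% | 4.6 points |
| 20% | 28.4% | 8.4 points |
| 40% | 53.5% | 13.5 points |

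For two or more treatments under a Poisson model, the 48- and 72-week percentages are 0.5% and 1.1%, 2.2% and 4.5%, and 9.4% and 17.9%.

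**Step 4. Carry-over to the prior-treatment columns.** The gap is (relapse share, prior teprotumumab − relapse share, prior placebo) × (p72 − p48). The documents give no shares, so two sets of assumptions are used.

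*(a) Shares chosen for illustration.* With 50% against 5%, the multiplier is 0.45 and the gap is 2.1, 3.8 or 6.1 points for p48 of 10%, 20% or 40%. With 30% to 70% against 5%, the gap runs from 0.25 × 4.6 = 1.2 to 0.65 × 13.5 = 8.8 points.

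*(b) Shares built from response rates in TED01RV* (Protocol 7.1.3.4.2: 29/42 on teprotumumab, 9/43 on placebo). These are overall, not proptosis, responses. It is further assumed that all eligible subjects enroll and that 10% to 50% of responders relapse.

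- 10% relapse: shares are 2.9/(2.9 + 13) = 18.2% and 0.9/(0.9 + 34) = 2.6%. Mean windows (72 − 24 × share) are 67.6 and 71.4 weeks.
- 50% relapse: shares are 14.5/(14.5 + 13) = 52.7% and 4.5/(4.5 + 34) = 11.7%. Mean windows are 59.3 and 69.2 weeks.

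The gap is 0.7 to 5.6 points. Across (a) and (b) it is roughly 1 to 9 points.

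**Step 5. The opposite limit.** Suppose the Table 9.1 restrictions held completely, with no TED treatment in non-responders between Weeks 24 and 48. Freely treatable time would be 48 weeks in both types. At equal rates the gap would be zero.

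**Step 6. A common cut-off at Month 18 (Week 72), under the same limit.** Non-responders would have 24 freely treatable weeks: 1 − (1 − p48)^(24/48) = 5.1%, 10.6% and 22.5%. Relapse subjects would show 10%, 20% and 40%. The artefact is about 5 to 17 points between enrollment types, in the opposite direction.

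**The case against.** The strongest objection is that the extra 24 weeks are not ordinary time at risk. They are the clinic follow-up, in which Table 9.1 restricts the treatments being counted. The stretch without clinic visits is 48 weeks for both types. This stands in large part. It makes the figures in Step 4 close to an upper bound. It is not a full answer, because SAP 8.1 provides for additional TED treatment during the Follow-Up Period, so the restriction is not expected to hold completely.

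The columns are also inferred. SAP 7.4.4 does not name them, SAP 6.1 states only a general rule, and the mock-ups are in a separate file (SAP 19). This stands as a caution: the shell could already contain rows by enrollment type, though nothing in the text or the table index calls for them.

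Durability is analysed elsewhere on a fixed time base, as sustained response at each follow-up visit in lead-in non-responders only. Listings of TED treatments are also planned. This limits the consequence but leaves the percentages in Table 14.1.4.1.2.4 unqualified.

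A reader might go further and infer that the counts differ through length of observation alone, or that cutting everyone at Month 18 would make them comparable. The documents support neither. Restrictions differ by type, and so does ascertainment (clinic visits against contacts six months apart). Step 6 shows that a common calendar cut-off can create an artefact of its own.

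**Conclusion.** The point holds in limited form. The 72- and 48-week windows follow directly from the schedule, and SAP 7.4.4 makes no allowance for them. The overall percentage combines the two windows whatever the enrollment mix, provided both types are present. Both periods are defined in the protocol; what is missing is a single horizon to which the combined figure refers.

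The prior-treatment columns are distorted only as far as their enrollment mix differs. That is likely, but the documents do not quantify it. The range of roughly 1 to 9 points rests on a constant rate common to everyone and on assumed relapse shares. Its top needs a 70% relapse share and a 40% treatment rate together. With the restrictions taken into account the true figure would probably be lower, and it could be near zero. The ratio of 1.5 describes scheduled time and should not be read as the inflation in the counts.

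The summary is descriptive, has no planned test, and is not among the efficacy, PK or safety endpoints in SAP section 4. The consequence is for interpretation only.

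**What to change.** In SAP 7.4.4 and Table 14.1.4.1.2.4:

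1. Present the summary by enrollment type, and by enrollment type within prior-treatment group where numbers allow. SAP 6.6 already suppresses subgroup tables with fewer than 5 subjects.
2. State the scheduled window after Week 24 for each type: 72 weeks (24 clinic, 48 contact) and 48 weeks (contact only).
3. Show the Follow-Up Period and the Follow-Up Contact Period separately as well as combined. The Follow-Up Period rows apply to lead-in non-responders only.
4. Optionally, add a supportive row counting to the Month 18 contact, which both types have. A footnote should say that treatment restrictions and ascertainment differ by type over that span. This row should not replace the others.

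The cost is a few lines of SAP text and one revised shell with smaller cells. No new data are needed and none are lost.

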7.5. PROTOCOL DEVIATIONS

Major protocol deviations will be summarized for the ITT Population by the number and percentage of subjects overall and category of deviation during the Treatment Period and Follow-Up Period, separately; by overall and treatment received in HZNP-TEP-301 study. All protocol deviations will be listed.

8. EFFICACY

Efficacy assessments will be performed for both eyes at each assessment time point; however, only the study eye will be used to assess the primary efficacy endpoint. All summaries of efficacy endpoints will be conducted based on ITT population.

8.1. PRIMARY EFFICACY ENDPOINT AND ANALYSIS

The primary efficacy endpoint is the proptosis responder rate (percentage of subjects with a ≥ 2 mm reduction from Study Baseline in proptosis in the study eye, without deterioration [≥ 2 mm increase] of proptosis in the fellow eye) at Week 24 in the ITT Population.

Proptosis assessments will be performed using a Hertel exophthalmometer provided by the Sponsor for consistency in measurement, and (except when strictly unavoidable) the same Hertel instrument and same observer should be used at each evaluation for the full duration of the study. Additionally, the same intercanthal distance (ICD) must be used on each occasion.

Proptosis will be measured for each eye at Day 1 and Weeks 6, 12, 18, and 24 (or PW) during the Treatment Period, and for HZNP-TEP-301 proptosis non-responders at Weeks 28, 36, 48 (or PW) during the Follow-Up Period. Measurements will be recorded on the Clinical Measures of Severity eCRF under exophthalmos.

Subjects missing the Week 24 evaluation will be considered to be treatment failures (non-responders) for the primary analysis. Further, subjects who prematurely discontinue study drug dosing prior to Week 21 during the Treatment Period will be analyzed as treatment failures (non-responders), unless an assessment at Week 24 (within the day range specified in Section 6.4) is available.

Descriptive summaries of responder results of study eye will be provided by treatment received in HZNP-TEP-301 and overall at Week 24.

In addition, descriptive summaries of responder results will be provided by treatment received in HZNP-TEP-301 for each visit in the Treatment Period and for HZNP-TEP-301 proptosis non-responders in the Follow-Up Period for the ITT Population, considering subjects missing the evaluations as treatment failures (non-responders). Similar summaries will also be provided separately for the fellow eye, and by subject enrollment type (subjects who were proptosis non-responders in HZNP-TEP-301, subjects who relapsed during the Follow-Up Period in HZNP-TEP-301), tobacco use status (non-user, user), region (US, EU), site, age group (<65 years, ≥ 65 years), gender, race (white, black or African American, Asian, other), and ethnicity (Hispanic or Latino, not Hispanic or Latino). A plot of proportion of proptosis responder by visits and treatment received in HZNP-TEP-301 will also be provided.

In addition, a separate analysis will be provided for time to proptosis response. Time to proptosis response will be measured as the days from the first dose date to the earliest visit date in which the criteria are met for proptosis response (≥ 2 mm reduction from Study Baseline in proptosis in the study eye, without deterioration [≥ 2 mm increase] of proptosis in the fellow eye) within the Treatment Period, calculated as:

first visit date in which criteria for proptosis response are met - first dose date + 1

Subjects not achieving a proptosis response within the Treatment Period will be censored at their last visit date with a proptosis assessment within the Treatment Period. Kaplan-Meier estimates will be provided by treatment received in HZNP-TEP-301 of the 25th percentile, median, and 75th percentile. 95% confidence intervals (CI) will be provided for the median. Analyses will be based on the ITT Population. Any ITT subject who is enrolled but not dosed will be censored at Day 0.

The analysis will be repeated for the fellow eye (using a definition analogous to the one used for the study eye).

Plots of the time to proptosis response will be provided by treatment received in HZNP-TEP-301 for the study eye and fellow eye.

Further, for subjects who were proptosis non-responders in HZNP-TEP-301, sustained proptosis response at a given visit in the HZNP-TEP-302 Follow-Up Period will be defined for HZNP-TEP-302 Week 24 proptosis responders as:

- ≥ 2 mm reduction from Baseline in proptosis in the study eye, without deterioration (≥ 2 mm increase) of proptosis in the fellow eye, AND
- No additional TED treatment received by the time of the visit.

Additional TED treatment will include any instances of TED medication (identified by manual listing review), TED concomitant procedures (identified by manual listing review), TED surgical procedures, and/or orbital radiation treatments.

At each assessment after Week 24, the proportion of subjects who are sustained responders will be summarized by treatment received in HZNP-TEP-301. Subjects who are missing proptosis values at a visit will be considered non-responders at that visit.

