Subject response in Study HZNP-TEP-301	Proptosis Non-responder or Relapse											Proptosis Non-responder Only			Relapse Only		Proptosis Non-responder Only	
Glucose 	X 	X	X	X	X	X	X	X	X	X	X		X	X				
HbA1c	X 						X					X		X	X			
Urinalysis	X 		X		X	X		X			X		X	X				
ADA/NAb samples 	X 		X		X						X 		X	X				
AE, SAE assessment 	X 	X	X	X	X	X	X	X	X	X	X	X	X	X				
Concomitant medications	X 	X	X	X	X	X	X	X	X	X	X	X	X	X				
GO-QoL Questionnaire	X 			X		X					X	X		X				
PK samples 	X	X	X	X		X					X 							
Contact (phone/email) to assess additional TED treatment 															X	X	X	X

ADA=anti-drug antibody; AE=adverse event; CAS=Clinical Activity Score; ECG=electrocardiogram; FT3=free triiodothyronine; FT4=free thyroxine; FU=Follow-Up; GO-QoL=Graves' Ophthalmopathy Quality of Life Questionnaire; HbA1c=glycated hemoglobin; M=month; NAb=neutralizing antibody; PK=pharmacokinetic; PW=premature withdrawal; SAE=serious adverse event; TED=thyroid eye disease; TSH=thyroid stimulating hormone; W=week.

Footnotes:

- Open-label Treatment Period. Subjects with TED who are proptosis non-responders at Week 24 of HZNP-TEP-301 or were proptosis responders at Week 24 but who meet criteria for re-treatment due to relapse during the Follow-Up Period in HZNP-TEP-301 are eligible to enroll and receive 8 infusions of teprotumumab (10 mg/kg for the first infusion titrated to 20 mg/kg for the remaining infusions) in an open-label fashion.
- Proptosis non-responders from Study HZNP-TEP-301 will participate in a 6-month Follow-Up Period; subjects who relapsed during the Follow-Up Period of HZNP-TEP-301 will not participate.
- Proptosis non-responders from Study HZNP-TEP-301 who complete the Month 12 Visit and subjects who relapsed during the Follow-Up Period of HZNP-TEP-301 and complete the Week 24 Visit will be contacted via phone or email by research staff to enquire if any treatment for TED has been received since last study contact.
- If subjects wish to discontinue study drug during the open-label Treatment Period, subjects will return for a clinic visit and undergo the Week 24 assessments, except for PK and ADA evaluations. Subjects who were proptosis non-responders at Week 24 of HZNP-TEP-301 will be encouraged to continue study participation in the Follow-Up Period.

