### **9.3.3 Removal of Subjects from Therapy or Assessment**

All subjects are free to withdraw from study participation at any time, for any reason, and without prejudice to their further medical care. In addition, the Investigator may terminate a subject from the study at any time. The primary reason for discontinuation from the study and/or study drug should be recorded on the eCRF using one of the following categories:

- Adverse Event. The subject experiences an AE that imposes an unacceptable risk to the subject's health, or the subject is unwilling to continue because of an AE. AEs requiring permanent study drug discontinuation per the protocol include:
  - A drug-related anaphylactic reaction.
  - A persistently severe drug-related AE that does not abate to mild or moderate intensity at least 2 weeks prior to the next scheduled dose.
  - Severe drug-related hyperglycemia (e.g., blood glucose > 250 mg/dL) that does not abate to mild or moderate intensity with anti-diabetic treatment (dose may be skipped up to 2 times prior to permanently discontinuing study drug; see [Section 9.4.6.3.2](#) for details).
  - Diagnosed or suspected IBD (e.g., diarrhea with or without blood or rectal bleeding associated with abdominal pain or cramping/colic, urgency, tenesmus, or incontinence for more than 4 weeks without a confirmed alternative diagnosis OR

endoscopic or radiologic evidence of enteritis/colitis without a confirmed alternative diagnosis).

- Lack of Efficacy. Removal of a subject from the study is at the discretion of the Investigator and may occur if the Investigator determines that study drug administration is not benefitting the subject and eye symptoms linked to progressing disease worsen posing an unacceptable risk to the subject. The specific care of the subject is best determined by the Investigator and managing physician(s) involved in the subject's care and may require removal from the study. All subjects are free to withdraw from study participation at any time, for any reason, allowing them to receive any specific treatment for TED that is considered necessary per their treating physician and local standard of care.
- Non-Compliance with Study Drug/Other/Protocol Deviations. The subject has a significant protocol deviation, does not comply with study drug administration schedule, or fails to adhere to other study requirements as stated in the protocol.

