**Table 9.1      Restricted Medications and Therapies**

Medication/Therapy	Restricted Dose or Time Period
Orbital irradiation for TED	Any history or planned procedure during entire study duration through Week 48 of Follow-Up Period.
Eye surgery for TED	Any history or planned procedure during entire study duration through Week 48 of Follow-Up Period.
Steroids for treatment of TED	Steroids (IV or oral) for treatment of TED and steroid eye drops are not allowed between Week 24 of the HZNP-TEP-301 protocol and Baseline/Day 1 of the HZNP-TEP-302 protocol through the end of study visit.
Steroids for conditions other than TED	Systemic steroid use (IV or oral) for conditions other than TED is not allowed during the study however topical steroids for dermatological conditions, inhaled steroids, and IV dexamethasone for infusion-associated AEs are allowed.
Non-steroid eye drops	Vasoconstrictor eye drops are not allowed during the study. Other non-steroid drops such as saline or methylcellulose are allowed but should not be used on the day of a clinic visit.
Selenium or biotin for TED	Selenium or biotin for TED is not allowed during the study. A multivitamin (taken maximally once daily) containing selenium and/or biotin is allowed.
Rituximab (Rituxan® or MabThera®) or tocilizumab (Actemra® or Roactemra®)	Any previous use or anticipated use during the study.
Non-steroid immunosuppressive agent (other than rituximab or tocilizumab)	Use of a non-steroid immunosuppressive agent is not allowed during the study.
Investigational agent	60 days prior to study entry through study completion.
Illicit drug/alcohol use	History of abuse within the past 2 years or abuse during study.

Hearing loss and/or ototoxicity is not considered to be an adverse event causally associated with the use of teprotumumab. However, it may be reasonable to avoid ototoxic medications such as systemic administration of aminoglycoside and platinum-based chemotherapy during the study.

The following medications may cause muscle spasm/cramps and should be avoided during the study: donepezil, neostigmine, and vincristine.

All concomitant treatment (for TED and other conditions) in the Treatment Period and the Follow-Up Period must be documented in the eCRF.

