8.2. SECONDARY EFFICACY ENDPOINTS AND ANALYSES

8.2.1. CAS Categorical Response

The CAS will be completed at Day 1 and Weeks 6, 12, 18, and 24 (or PW) during the Treatment Period, and for HZNP-TEP-301 non-responders at Weeks 28, 36, 48 (or PW) in the Follow-Up Period using the 7 item European Group on Graves' Ophthalmopathy (EUGOGO) amended CAS (Mourits et al, 1989) for each eye.

For each item present, one point is given. The sum of these points is the total score.

- Spontaneous orbital pain
- Gaze evoked orbital pain
- Eyelid swelling that is considered to be due to active (inflammatory phase) TED/GO
- Eyelid erythema
- Conjunctival redness that is considered to be due to active (inflammatory phase) TED/GO (ignore "equivocal" redness)
- Chemosis
- Inflammation of caruncle or plica

The first secondary endpoint is CAS as a categorical response variable defined as a reduction to a CAS of 0 or 1 from Study Baseline at Week 24. Subjects missing the Week 24 evaluation will be considered to be treatment failures (non-responders) for the analysis. Descriptive summaries of responder results will be provided for the study eye and fellow eye by treatment received in HZNP-TEP-301 for the ITT Population at Week 24. Only subjects with CAS > 1 at study baseline in the ITT Population will be summarized.

In addition, descriptive summaries of responder results will be provided for the study eye and fellow eye by treatment received in HZNP-TEP-301 for the ITT Population for each visit in the Treatment Period and for HZNP-TEP-301 proptosis non-responders in the Follow-Up Period, considering subjects missing the evaluations as treatment failures (non-responders). Similar summaries will also be provided separately by subject enrollment type (subjects who were proptosis non-responders in HZNP-TEP-301, subjects who relapsed during the Follow-Up Period in HZNP-TEP-301), tobacco use status (non-user, user), region (US, EU), and site. The proportion of subjects with a complete CAS response (subjects who have a CAS of 0) in the study eye will be summarized for each visit in the Treatment Period and Follow-Up Period considering observed results only. Only subjects with CAS > 0 at study baseline in the ITT Population will be summarized.

Summaries after Week 24 for subjects who were proptosis non-responders in HZNP-TEP-301, will also include a summary of sustained CAS response, where sustained responder

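### Follow-Up by-visit responder rates ignore additional TED treatment, so a Week 24 non-responder who is treated, stays and improves counts as a responder

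*SAP*

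**What the plan says.** **By-visit rule.** For lead-in proptosis non-responders, SAP 8.1 gives proptosis response at each Follow-Up visit (Weeks 28, 36 and 48) "in the Follow-Up Period for the ITT Population, considering subjects missing the evaluations as treatment failures (non-responders". SAP 8.2.1 words the CAS rule in the same way, "in the Follow-Up Period, considering subjects missing the evaluations as treatment failures (non-responders", and the wording recurs for diplopia (8.2.3) and overall response (8.3.1). None of the four states a condition on other TED treatment.

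**Sustained response.** SAP 8.1 does use such a condition elsewhere. Sustained proptosis response "will be defined for HZNP-TEP-302 Week 24 proptosis responders as" the measurement criterion plus "No additional TED treatment received by the time of the visit". Sustained CAS (8.2.1), diplopia (8.2.3) and overall response (8.3.1) are likewise tied to Week 24 status. The exception is the 'No diplopia' summary in 8.2.3, which applies the condition whatever the Week 24 value was, but only counts a score of 0.

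**Restrictions and withdrawal.** Protocol Table 9.1 restricts orbital irradiation and eye surgery for TED: "Any history or planned procedure during entire study duration through Week 48 of Follow-Up Period". On steroids it says "Steroids (IV or oral) for treatment of TED and steroid eye drops are not allowed between Week 24 of the HZNP-TEP-301 protocol", and the bar runs on to the end of study visit. Protocol 9.3.3 leaves subjects free to withdraw, "allowing them to receive any specific treatment for TED that is considered necessary per their treating physician and local standard of care". Under protocol 9.7, continuation after a deviation is decided case by case. A footnote to the schedule (protocol 2.1) on stopping study drug early adds: "Subjects who were proptosis non-responders at Week 24 of HZNP-TEP-301 will be encouraged to continue study participation in the Follow-Up Period".

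**Withdrawal visits.** SAP 6.4 assigns a premature-withdrawal visit to the nearest scheduled visit, unless data from that scheduled visit already exist.

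**The concern.** The study has no control arm. In a by-visit row, a Week 24 non-responder who improves at Week 36 after surgery or steroids looks the same as one with a late response to teprotumumab. The SAP evidently regards additional TED treatment as relevant after Week 24, since it builds it into every sustained-response definition. It does not carry the condition to the group in which a late change of status would be most open to that confusion.

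The rule also partly ties scoring to attendance. A treated subject who stays is scored on the measurement at every visit attended. One who withdraws for the same treatment becomes a non-responder at visits with no data. At stake is the reading of a few descriptive Follow-Up percentages and their plots.

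**Working it through.** The documents give no Follow-Up group size, no rate of additional treatment and no figure to reproduce. The check is a trace of the rules, followed by one line of arithmetic.

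**Trace.** Take lead-in non-responders who are also non-responders at Week 24 of this study and who turn to the same additional TED treatment during Follow-Up.

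- *Stays, and shows a reduction of 2 mm or more without fellow-eye deterioration at Weeks 36 and 48.* Responder at both visits (SAP 8.1). Not in the sustained-response analysis, because not a Week 24 responder.
- *Leaves before any Follow-Up visit, with no withdrawal visit in that period.* Missing, hence non-responder, at Weeks 28, 36 and 48.
- *Leaves with a withdrawal visit on Day 177 to 225.* That visit becomes Week 28 and is scored as measured; non-responder at Weeks 36 and 48.
- *Withdrawal visit on Day 226 to 295.* Becomes Week 36 and is scored as measured; non-responder at Week 48.
- *Withdrawal visit on Day 296 or later.* Becomes Week 48 and is scored as measured; there is no later visit to fail.

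The last three lines assume that no scheduled data exist for the assigned visit. The contrast between staying and leaving is therefore real only at visits after the one to which the withdrawal visit is assigned.

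**Does another summary show the first subject?** For proptosis, CAS and overall response, no treatment-conditioned summary includes a Week 24 non-responder. For diplopia, 'No diplopia' does, but not for a drop of one grade that stops short of 0.

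**Direction.** Adding the condition can only remove responders. The as-measured rate is therefore at or above the conditioned rate.

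**Size.** Let n be the denominator of the summary in one lead-in treatment group, and k the number of treated subjects who meet the criterion only because of the additional treatment. Shift = 100 × k / n points. With k = 1:

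- n = 10: 100 × 1 / 10 = 10.0 points
- n = 20: 100 × 1 / 20 = 5.0 points
- n = 30: 100 × 1 / 30 = 3.3 points

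All three n, and k, are assumptions. The CAS, diplopia and overall summaries restrict n further by baseline status (SAP 8.2.1, 8.2.3, 8.3.1), so one subject moves those rates by at least as much.

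**The case against.** The strongest reply is that this is rare and of little consequence. Table 9.1 restricts surgery, irradiation, TED steroids, rituximab, tocilizumab, other immunosuppressants, and selenium or biotin for TED. The event therefore needs a deviation, in a subject who is kept in the study, does not withdraw, and then meets the criterion. The tables carry no test or decision rule. A reader could also trace each such subject through the planned summary of additional TED treatments (SAP 7.4.4), the deviation listings (7.5) and the response listings. All of that stands, and it keeps the point small. It does not answer it, because none of those outputs changes or annotates the by-visit rate.

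A second reply is that scoring regardless of other treatment is a legitimate descriptive choice. That also stands. But the SAP does not label the rate so, and the failure rule for missing visits means that it is not applied uniformly.

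Three stronger readings are tempting, and the documents do not support them:

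- *Withdrawal always means failure.* SAP 6.4 scores the withdrawal visit as measured at its assigned visit.
- *Encouraging early stoppers to continue in Follow-Up means that they receive other treatment.* The footnote concerns attendance only.
- *The as-measured rate overstates the drug effect.* It is higher only relative to the conditioned rate, which in turn fails subjects who would have responded anyway.

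**Conclusion.** The point holds as a gap in supportive summaries. In the Follow-Up by-visit tables for proptosis, CAS, diplopia and overall response, a Week 24 non-responder who has additional TED treatment, remains in the study and then meets the criterion is counted as a responder. No treatment-conditioned proptosis, CAS or overall summary reveals it. Few subjects are likely. The per-subject shift of 3.3 to 10.0 points rests on assumed denominators of 30 down to 10.

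A reader might infer that the headline response rate is inflated. It is not: every primary, secondary and exploratory efficacy endpoint is read at Week 24, and treatment given in Follow-Up cannot alter it. This is an optional improvement, held with medium confidence because neither the denominators nor the frequency of additional treatment can be known from the documents.

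**What to change.** In the main, non-subgroup by-visit tables for the four responses, add one row at each Follow-Up visit that counts a subject as a non-responder once additional TED treatment has been received, regardless of Week 24 status. Use the SAP 8.1 sustained-response definition and flag unchanged, so that the by-visit and sustained tables agree. Keep the as-measured rate beside it, labelled 'regardless of additional TED treatment', and label the by-visit plots in the same way. Leave the Week 24 definitions and the subgroup tables as they are. No separate treatment definition and no analysis of treatment before Week 24 is needed.

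The cost is low. The index lists two such tables each for proptosis, CAS and diplopia (Study Baseline and HZN-001 Baseline) and one for overall response, so 2 + 2 + 2 + 1 = 7 tables gain the row. The text accompanying protocol Table 9.1 already requires concomitant TED treatment to be recorded in the eCRF, and SAP 7.4.2 and 7.4.3 already plan the manual review of TED medications and procedures in the Follow-Up Period.

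The downside is that the conditioned rate may be slightly less favourable and fails any treated subject who would have responded anyway. Showing both rates makes the difference visible.
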